## 4 Study Design

---

This is a prospective, multi-center, open label, bilateral wear, one week dispensing study comparing the clinical performance of the MyDay Sphere lenses following a refit with MyDay Energys lenses.

Habitual wearers of MyDay Sphere lenses will be reviewed at Visit 1 to ensure optimal visual acuity is being achieved. If the visual acuity and power of the habitual MyDay Sphere lens is optimal, the participant will continue to wear MyDay Sphere in the same prescription for at least 7 days after which baseline variables will be collected. If an amendment of the power of the habitual MyDay Sphere is required, participants will be dispensed with the new power of the MyDay Sphere lenses to be worn for at least 7 days. In the instance where the participant habitually wears lenses which are not MyDay Sphere, the participant will be fit and dispensed MyDay Sphere lenses to be worn for at least 7 days.

After wearing MyDay Sphere lenses for at least 7 days in the study, all participant will return for baseline variables to be evaluated and will be then be dispensed with MyDay Energys. The participant will be asked to return for evaluation after 7-10days of lens wear. Participants will exit the study following the final evaluation of MyDay Energys.

This study will be open label. Over labeling of the blister packs is not required.

[figure not shown]

Figure 1 Study flow chart.

[figure not shown]
## 5 Study Population

---

### 5.1 Sample Size Calculation

A sample size calculation was made based on the primary outcome variable of lens fit acceptance grade, using data from a previous study: EX-MKTG-63. In this previous study the lenses compared were Biofinity and Biofinity Energys and for lens fit acceptance the difference between mean results

was 0.16, with a standard deviation of not greater than 0.4. For alpha 0.05, a sample size of 73 provides power of 92%. This variable will be graded using a 0-4 scale with 0.5 steps. Therefore, to allow for drop-outs and protocol deviations affecting inclusion in the analysis cohort, dispensing to 80 participants will be targeted.

## 6 Investigational Sites

### 6.1 Number of Sites

This study design considers 5 sites and 80 subjects to complete the study.

### 6.2 Investigator Recruitment

The principal investigator and co-investigators at each site will be required to fulfil the following criteria:

- Licensed Optometrist with at least two years of contact lens fitting experience.
- Experienced Investigators who will be trained in Good Clinical Practice (GCP) by the already trained principal investigator.
- In-office email and either document scanning capabilities or fax.
- Willingness to follow the study protocol and to co-operate with the study monitors.

This clinical study is designed to be in conformance with the ethical principles in the Declaration of Helsinki, with the ICH E6 guidelines for Good Clinical Practice (GCP) and all the applicable local guidelines.

## **7 Ethics Review / Statement of Compliance**

---

### **7.1 Relevant Standards / Guidelines**

---

This implementation document has been developed in accordance with the following:

- ICH E6- International Conference on Harmonization: Good Clinical Practice (GCP)
- Declaration of Helsinki

### **7.2 Institutional Review Board**

---

This study will be conducted in accordance with Institutional Review Board regulations (U.S. 21CFR Part 56.103) or applicable IEC regulations. Copies of all IRB/IEC correspondence with the investigator/sponsor will be kept on file. The study will commence upon approval from the following Institutional Review Board: Sterling Institutional Review Board; [contact] and email address: [contact].

### **7.3 Clinical Trial Registration**

---

This study will be registered with clinical trials.gov in accordance with section 801 of the Food and Drug Administration (FDA) Act which mandates the registration of certain clinical trials of drugs and medical devices.

### **7.4 Informed Consent**

---

Informed consent shall be obtained in writing from the subject and the process shall be documented before any procedure specific to the clinical investigation is carried out.

## **8 Potential Risks and Benefits to Human Subjects**

---

There may be direct benefits to the subjects in this study, such as improved vision and/or comfort. Participation in a study may contribute to scientific research information that may be used in the development of new contact lens products. In addition, subjects will receive an examination of the front part of their eyes and may have the opportunity to try a different type of soft contact lenses and/or different lens care products at no cost to them. The contact lens materials used in this study are commercially available as daily wear. This study will investigate participants' wearing schedule

intended for daily wear (NOT extended wear), similar to the average wearing time of 10-16 hours for daily wear lenses.

This study is considered to be a non-significant risk study based on United State Food and Drug administration (FDA) and International Standards Organization (ISO) guidelines, because the study devices used as intended in this study (1) do not represent a potential for serious risk to the health, safety or welfare of the subject, and (2) are not implants, (3) are not used to support or sustain human life, (4) are not of substantial importance in diagnosing, curing, mitigating or treating disease or otherwise prevents impairment of human health.

Complications that may occur during the wearing of contact lenses include discomfort, dryness, aching or itching eyes, excessive tearing, discharge, hyperemia and variable or blurred vision. More serious risks may include pain, photophobia, iritis, corneal edema or eye infection. Although contact lens-related infections are very infrequent, the possibility does exist. The incidence of infection due to day-wear soft lenses is 0.035%. Almost always an infection will occur only in one eye. This risk is assumed by 35-million Americans who currently wear contact lenses and only current soft lens wearers will be recruited for this study.

Routine clinical procedures including auto-refraction, auto-keratometry, visual acuity, anterior ocular health assessment, and contact lens fitting will be used. In addition, high magnification imaging of the lens fit may be made using 35 mm or digital cameras. Patients will be monitored frequently until the end of the study to reduce the occurrence of adverse or potential adverse events. Patients will be given instructions from their investigator regarding early symptoms and signs of adverse events.

## **9 Materials and Methods**

---

### **9.1 Participants**

---

Up to 120 subjects may be screened for this study. All potential subjects will be habitual wearers of MyDay Sphere or will be adapted to this lens for at least one week as part of the study. Each subject will be required to attend up to six study visits scheduled on three days over a period of approximately 2-3 weeks.

Each subject will be given a unique ID number. All subjects who sign a consent document will be included in the subject enrollment log which will include; subject ID, date of consent, date of screening, date of study completion, date of discontinuation (if required), reason for discontinuation (if required).

Additionally, all subjects must meet the study inclusion and exclusion criteria listed below.

#### **Inclusion criteria**

A person is eligible for inclusion in the study if he/she:

- Is between 18 and 35 years of age (inclusive)
- Has read and signed the informed consent letter
- Is willing and anticipated to follow instructions and maintain the appointment schedule
- Habitually wears soft spherical contact lenses with a power between -1.00D to -6.00D (inclusive) for a minimum 5 days per week, 10 hours per day and anticipates no difficulty wearing contact lenses for 7 days per week, 10 hours per day.
- Habitually wears or is able to be adequately refit into MyDay Sphere lenses
- Demonstrates an acceptable fit with the study lenses
- Is correctable to a distance visual acuity of 0.20 logMAR (approximately 20/30) or better (in each eye) with the study contact lenses
- Uses digital devices, (e.g. computer, tablet, smart phone, iPad), for more than 4 hours a day, 5 days a week.
- Manifest cylindrical spectacle refraction does not exceed -0.75DC in either eye
- Has clear corneas and no active ocular disease
- Has a contact lens refraction that fits within the available parameters of the study lenses.

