## 2 Study Objective

---

[figure not shown]
The aim of this study is to determine if habitual or adapted wearers of MyDay Sphere lenses can be confidently refit into MyDay Energys lenses and be successful after one week of daily wear.

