**Primary outcomes:**

- Overall lens fit acceptance grade (Appendix 9)

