### 9.2.1 Contact lenses

All subjects will be trial fitted and, if suitable, dispensed the MyDay Sphere and the MyDay Energys lens brand. The study lenses will be provided by the Sponsor. Details of the contact lenses are shown in Table 1.

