### **9.3.1 Visit 1: Screening and establish optimum power of MyDay Sphere**

Participants will attend a screening visit during which the subject will be required to read and sign an informed consent for prior to enrolment. When the subject has signed the consent form, the subject will be considered to be enrolled in the study. The investigator should also sign the consent form. The subject will be provided with a copy of the consent and the original will be kept in the subject's paper chart. It may also be scanned into the subject's electronic medical record (EMR) file.

Participants will be assigned a study ID number when they sign the informed consent document, and before their eligibility for the study has been confirmed. Subjects must be enrolled sequentially. The subject enrollment log will be updated. Ineligible participants will be discontinued from the

study. Depending on the participant's habitual lens type, participants may follow the following procedures and visits outlined (illustrated in Figure 2).

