**Figure 2: Flow chart for participants depending on habitual lens type.**

#### **Habitual MyDay Sphere wearers (Visit 1):**

Participants that habitually wear MyDay Sphere lenses will attend Visit 1 wearing their own MyDay Sphere lenses for **at least 2 hours** prior to the visit.

Data to be collected:

- Participant demographics, including Race and Ethnicity
- Habitual contact lens type and prescription
- Wearing times with habitual lenses:
  - Wearing time today (hours).
  - Average daily wearing time (hours/day)
  - Number of days/week (lenses are worn)
- Health and medication.

- [REDACTED]
- [REDACTED]
- Remove contact lens
- Automated refraction and keratometry
- [REDACTED]
- If at this point the subject is found to be ineligible, then complete an Exit form and exit the subject from the study.
- Eligibility will be confirmed and the participant continues right away with **Visit 2**

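### Acceptable fit and acuity with the test lens are entry criteria, so people whom MyDay Energys does not fit drop out of a trial about refitting into it

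*Combined protocol and SAP*

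**What the plan says.** The inclusion criteria in Section 9.1 require that a person "Demonstrates an acceptable fit with the study lenses" and "Is correctable to a distance visual acuity of 0.20 logMAR (approximately 20/30) or better (in each eye) with the study contact lenses". Neither names a lens or, for fit, a grade. Section 9.1 makes every listed criterion binding. Table 1, which defines the study lenses, has two columns: MyDay Sphere (control) and MyDay Energys (test). A separate inclusion bullet already deals with suitability for Sphere alone.

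Section 2 makes the overall fit acceptance grade the primary outcome and states the aim as whether wearers "can be confidently refit into MyDay Energys lenses and be successful after one week of daily wear".

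On sequence, Section 9.2.1 says "All subjects will be trial fitted and, if suitable, dispensed the MyDay Sphere and the MyDay Energys lens brand". In Section 9.3.1, for habitual Sphere wearers, "Eligibility will be confirmed and the participant continues right away with" Visit 2, and the text for wearers of other lenses says the same. Energys is fitted at Visit 4 (Section 9.3.4), after at least 7 days of Sphere. Table 2 nevertheless allows a longer Visit 1 if both lenses are fitted then. Section 11.1 analyses participants who were evaluated and excludes missing data points.

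**The concern.** A person who is acceptable in Sphere but not in Energys is a failed refit, the event that the stated aim is about. Read with Table 1, the entry criteria make such a person ineligible. The criterion and the primary outcome are the same construct, measured at fitting and again after 7 to 10 days of wear.

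The timing is also unsettled. If Energys fit is judged at Visit 1, the trial pre-selects eyes that suit Energys. If it is judged at Visit 4, a refit failure can be relabelled as an eligibility failure or simply not dispensed. Either way the person has no Visit 5 grade and is absent from the paired comparison. Section 5.1 sets its target as 80 people dispensed to, and Section 9.1 allows up to 120 to be screened, so failures before dispensing need not appear in any planned result. The conclusion would then describe people already shown to fit Energys, which is narrower than the habitual or adapted Sphere wearers named in the aim.

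**Working it through.** **1. Does the criterion reach Energys?** Table 1 puts both lenses under the term that the criteria use. Because Sphere suitability has its own bullet, the fit bullet is not just another way of saying Sphere. On the text, yes.

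**2. The plan's own figure.** Section 5.1 gives a difference of 0.16, an SD of at most 0.4, alpha 0.05 and n = 73. Taking the SD as that of paired differences, the noncentrality is 0.16/0.4 × √73 = 3.42. A two-sided paired t-test with 72 degrees of freedom then has power 92.1%, which matches the stated 92%. Nothing here disputes the sample size; 0.16 and 0.4 serve only as yardsticks.

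**3. Simple arithmetic on assumed inputs.** Suppose Energys equals Sphere (mean grade 3.5) in those it fits, and a fraction f whom it does not fit would grade g. Including them shifts the mean difference by f × (g − 3.5).

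| f | g = 1.0 | g = 2.0 |
|---|---|---|
| 2% | −0.05 | −0.03 |
| 5% | −0.125 | −0.075 |
| 10% | −0.25 | −0.15 |

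To hide a difference of 0.16, f must be 0.16/2.5 = 6.4% (g = 1.0) to 0.16/1.5 = 10.7% (g = 2.0).

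**4. Simulation on assumed inputs.** Sphere grades have mean 3.0 to 3.4 and between-person SD 0.5 to 0.6. The true Energys minus Sphere difference is −0.16 (planning size, sign assumed). Grades are rounded to 0.5 and limited to 0–4, and unacceptable means ≤1.5 or ≤2. Selection on first Sphere fit alone is compared with selection on both first fits.

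| | Set A | Set B |
|---|---|---|
| Person-by-lens SD | 0.33 | 0.15 |
| Visit noise SD | 0.15 | 0.22 |
| Resulting paired SD | 0.41–0.44 | 0.37–0.40 |
| Shrinkage of mean difference | about 2–30% | about 0–7% |
| Largest case | −0.16 to −0.114 | −0.154 to −0.144 |
| Fall in unacceptable Energys rate at one week | up to about 70% | about 33–50% |

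Set A screens out 0.7% to 12.3% of Sphere-acceptable people. In one of its scenarios the unacceptable rate falls from 4.5% to 1.5%. Its paired SD lies slightly above the 0.4 bound in Section 5.1; Set B respects that bound.

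A third model treats the two lenses' grades in one person as unrelated. With 6% failing, it moves the difference from about −0.13 to between −0.10 and −0.06. It implies a paired SD of √2 × 0.7 = 0.99 before rounding and capping, far above 0.4, so I leave it out of the range.

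**5. What rewording alone would do.** The unselected side of step 4 gives one-week grades to people whose first Energys fit was unacceptable. Under Section 9.2.1 they would normally not be dispensed the lens, and under Section 11.1 their missing Visit 5 point is excluded. With the criteria limited to Sphere and nothing else changed, the same people are still missing from the paired comparison. Step 4 therefore measures the distance from the whole Sphere-eligible population, not what a wording change would recover.

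**The case against.** The strongest reply is that the loss comes from conditional dispensing and the handling of missing data, so the eligibility wording makes little difference. That stands as far as the paired comparison goes, and it is why the fix has to go beyond wording. It does not clear the criterion, which classes a failed refit as ineligible and so gives a reason not to count it.

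Second, Table 1 gives both lenses the same material, water content, base curve, diameter and power range, so failures may be rare. This stands as a limit on size. The sponsor did plan on a 0.16 difference between another sphere lens and its Energys counterpart, so a difference was not thought negligible.

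Third, parts of the Visit 1 and Visit 4 procedures are redacted, and handling of an unacceptable Energys fit may be described there. A reader might infer that a site must discontinue such a person. The published text does not establish that: the sentence "Ineligible participants will be discontinued from the" study belongs to Visit 1, and the visible schedule fits Energys at Visit 4. Failures would also leave a trace, since the enrolment log and the exit form record reasons for discontinuation. A trace in a log is still not a planned result.

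Fourth, Sphere grades are truncated too. Sphere is the required starting lens, so that selection fits the aim; selection on Energys does not.

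**Conclusion.** The point holds at moderate severity. As written, the plan selects at entry or at first Energys fitting on an earlier measurement of its primary outcome, and no visible text counts the people removed. The timing in Sections 9.1, 9.2.1, 9.3.1 and 9.3.4 and Table 2 must be reconciled.

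The size is unknown. The documents give no failure rate, mean grade, between-person SD, cut-off for acceptable fit or sign of the difference. On the assumed inputs the mean difference shrinks by about 0% to 30% and the apparent unacceptable-fit rate falls by about a third to 70%. Effects are small if failures are rare.

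Two stronger readings are not supported. One is that the Visit 5 Energys grades are cut off at the lower end. Selection is at first fit, and Visit 5 still allows grades from 0 to 4 and asks for a reason at 2 or below, so low grades become fewer but are not impossible. The other is that a reported refit success rate is inflated. The visible plan defines no refit proportion, only a difference in grade.

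**What to change.** 1. In Section 9.1, limit the fit and acuity inclusion criteria to MyDay Sphere. In Section 9.3.1, confirm eligibility after the Sphere fit, in both the text for habitual Sphere wearers and the text for wearers of other lenses. Align Table 2 and Section 9.3.4 with this.
2. Record the overall fit acceptance grade at the first Energys fitting for everyone fitted, and state which grades count as unacceptable.
3. With the primary result, report the number and proportion of Sphere-eligible participants who had an unacceptable first Energys fit or were not dispensed Energys, counted as unsuccessful refits.
4. Add a sensitivity analysis of the paired difference that uses the first-fit Energys grade where there is no Visit 5 grade. These grades are selected for being low, so this analysis may lean somewhat against Energys; present it beside the main comparison, not in its place.

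Dispensing decisions stay as the protocol already provides.

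The cost is one added descriptive endpoint, one sensitivity analysis and, if not already collected in the redacted Visit 4 text, one grade on the form. No extra visit or participant is needed, and the sample size is unaffected. The Energys result may look slightly less favourable. The grade should be recorded during the study, because someone excluded without an Energys grade cannot be recovered at analysis.

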### **Exclusion Criteria**

A person will be excluded from the study if he/she:

- Is participating in any concurrent clinical research study
- Has a history of not achieving comfortable CL wear (5 days per week; > 8 hours/day)
- Has a systemic condition that, in the opinion of the investigator, may affect the study measures
- Is using any systemic or topical medications that in the opinion of the investigator may affect the study measures.
- Presents with slit lamp findings or clinically significant anterior segment abnormalities that would contraindicate contact lens wear such as:
  - Pathological dry eye or associated findings
  - Significant pterygium, pinguecula, or corneal scars within the visual axis
  - Neovascularization > 0.75 mm in front of the limbus
  - Giant papillary conjunctivitis (GCP) worse than grade 1
  - Anterior uveitis or iritis (or history in past year)
  - Seborrheic eczema of eyelid region, Seborrheic conjunctivitis
  - History of corneal ulcers or fungal infections
  - Poor personal hygiene
- Has a known history of corneal hypoesthesia (reduced corneal sensitivity)
- Has a known sensitivity to the diagnostic pharmaceuticals to be used in the study
- Has aphakia, keratoconus or a highly irregular cornea.
- Has presbyopia or has dependence on spectacles for near work over the contact lenses.

- Has undergone refractive surgery.
- Is pregnant, lactating or planning a pregnancy (by verbal communication) at the time of enrolment
- Has participated in any other type of eye related clinical or research study within the last 7 days
- Is habitually using rewetting/ lubricating eye drops (more than once per day)

## 9.2 Study Materials

---

### 9.2.1 Contact lenses

All subjects will be trial fitted and, if suitable, dispensed the MyDay Sphere and the MyDay Energys lens brand. The study lenses will be provided by the Sponsor. Details of the contact lenses are shown in Table 1.

**Table1: Study lenses**

Brand	MyDay Sphere (Control)	MyDay Energys (Test)
Manufacturer	CooperVision	CooperVision
Material	stenfilcon A	stenfilcon A
Water Content	54%	54%
Base Curve	8.4	8.4
Lens Diameter	14.2	14.2
Lens Powers Sphere	-1.00 to - 6.00 (0.25 steps)	-1.00 to - 6.00 (0.25 steps)
Replacement schedule	Daily disposable	Daily disposable

### 9.2.2 Contact Lens care

No lens care systems are required as this study involves the use of daily disposable contact lenses.

### 9.2.3 Rewetting/ lubricating eye drops

Participants will be asked not to use rewetting/ lubricating eye drops during the study.

### 9.2.4 Storage of Study Medications/Treatments

There are no unapproved investigational products, medications or treatments used in this study requiring special storage accommodations. Room temperature storage is recommended for all study products.

### **9.2.5 Clinical Supply Inventory**

There are no unapproved investigational products used in this study requiring special inventory requirements. Study product will be accounted for using the product accountability forms provided to each site by CooperVision.

### **9.2.6 Disposal of Consumables**

This study dispenses consumables (lenses) to participants for use during the study. MyDay Sphere lenses will be dispensed for use over at least 1 week, MyDay Energys lenses will dispensed for use over approximately 1 week. All unused lenses will be collected and returned to the sponsor.

### **9.2.7 Masking and Control of Study Materials**

The study contact lenses will be not be masked to the participant. Study lenses will be dispensed in blisters without the lens box. The investigator will not be masked.

